Appendix E ASBMT RFI 2017 – Disease Classifications Corresponding to CIBMTR Classifications

ASBMT Diagnosis Category	ASBMT RFI Classification	CIBMTR Classification [^]
AML and ALL precursor B-lymphoblastic lymphoma/leukemia {per W.H.O. reclassified from lymphoma} precursor T-lymphoblastic lymphoma/leukemia	Low risk: CR 1	First complete remission (CR1): A treatment response where all of the following criteria are met for at least four weeks* [†] : 
 • Hematological: no blast cells in the peripheral blood, < 5% blasts in the bone marrow, no blasts with Auer rods (AML only), normal maturation of all cellular components in the marrow, normal CBC and ANC of > 1,000/μL • Platelets \geq 100,000/μL*[†] • Transfusion independent • No other signs or symptoms of disease, including extramedullary disease(e.g., central nervous system or soft tissue involvement) 
 • Include recipients with persistent cytogenetic abnormality who otherwise meet all the criteria of CR. CIBMTR collects information about cytogenetic and molecular testing for those in CR (hematologic CR), however these are only relevant for RFI reporting in as much as the centers judge importance of residual cytogenetic abnormalities in determining current status beyond the hematic criteria. • *In some cases, there may not be a four-week interval between the completion of treatment for disease and the disease assessment immediately prior to the HSCT. If this is the case, CR should still be reported as the status at transplantation. Although this is an exception to the general condition that CR is “durable” beyond four weeks, the status of CR represents the “best assessment” prior to HSCT. Similarly, sufficient time may not have elapsed to allow for platelet recovery to normal levels and physician judgment is required to interpret whether residual low platelet counts may reflect residual disease. 
 
NOTE: Recipients with MDS that transformed to AML If the recipient has residual MDS following treatment for AML, report the AML disease status as either PIF or relapse (i.e., the recipient cannot be in an AML CR if there is evidence of MDS at the time of assessment).
 

AML and ALL (con“t)	Intermediate risk: CR2, CR3+	Complete remission 2nd or greater (CR2/+)[†]: Recipient achieved CR as defined above, relapsed and achieved CR again. Final pre-HSCT status must be CR.
AML and ALL (con“t)	High risk (not in remission):	Never treated: The recipient was diagnosed with acute leukemia and never treated. For example, this disease status may be appropriate if MDS was initially diagnosed and

CONFIDENTIAL

ASBMT Diagnosis Category	ASBMT RFI Classification	CIBMTR Classification [^]
	Never treated Primary Induction Failure (PIF) Relapse	
treated, the MDS then transformed into AML, and a decision was made to proceed immediately to transplant instead of treating the AML with therapy.
 
Primary Induction Failure (PIF): The recipient was treated for acute leukemia but never achieved durable* complete remission with any therapy (*including relapsed < 1 mo from CR1 determination). The term “PIF” is not limited to the number of treatments used unsuccessfully.
 
Relapse: Recurrence of disease after CR. Relapse is defined as:
 
 • $\geq 5\%$ blasts in the marrow • Extramedullary disease • Reappearance of cytogenetic abnormalities and/or molecular markers associated with the diagnosis that, in the judgement of a physician, are at a level representing relapse. • Although CIBMTR collects information upon the number of the relapse, this information is not needed for the ASBMT RFI

Source: https://higherlogicdownload.s3.amazonaws.com/ASBMT/43a1f41f-55cb-4c97-9e78-c03e867db505/UploadedImages/ASBMT_RFI_2018B_CIBMTR_Disease_Classifications.pdf

CONFIDENTIAL

STUDY DRUG: QUIZARTINIB
 PROTOCOL DATE: 10 AUGUST 2020

DEVELOPMENT INNOVATIONS STUDY NUMBER: AML 48
 VERSION 4.0

Appendix F Management of Quizartinib-Associated Adverse Events

QTcF (QT interval corrected with Fridericia's formula) Prolongation

- Grade 1
 - Check magnesium and potassium levels and correct any abnormalities. If possible, stop any medications that may prolong the QTc interval. Continue quizartinib at the same dose.
- Grade 2 (QTcF average of triplicate readings >480 msec)
 - Check magnesium and potassium levels and correct any abnormalities. If possible, stop any medications that may prolong the QTc interval.
 - The dose will be reduced without interruption (See Table 2). Following dose reduction, the quizartinib/placebo dose may be resumed at the previous level in the next cycle if the QTcF has decreased to within 30 msec of baseline or <450 msec but subject must be monitored closely for QT prolongation for the first cycle at the increased dose.
 - If 20 mg/day is the current dose, dosing will be interrupted for up to 14 days. If QTcF returns to within 30 msec of baseline or ≤450 msec within 14 days, treatment may be resumed at 20 mg/day.
- Grade 3 (QTcF average of triplicate readings >500 msec)
 - Check magnesium and potassium levels and correct any abnormalities. If possible, stop any medications that may prolong the QTc interval.
 - Dosing will be interrupted for up to 14 days. If QTcF returns to within 30 msec of baseline or ≤450 msec within 14 days, treatment may be resumed at a reduced dose (See Table 2).
 - If 20 mg/day is the current dose, dosing will be interrupted for up to 14 days. If QTcF returns to within 30 msec of baseline or ≤450 msec within 14 days, treatment may be resumed at 20 mg/day. If Grade 3 event returns, treatment will be discontinued.
- Grade 4 (QTcF >500 msec or >60 msec change from baseline, and Torsade de pointes or polymorphic ventricular tachycardia or signs/symptoms of serious arrhythmia)
 - Treatment will be permanently discontinued.

Differentiation Syndrome

- Patients with suspected differentiation syndrome should promptly start treatment with systemic glucocorticoids and hemodynamic monitoring per local principal investigator or institutional preference until improvement. Treatment should be held until resolution to < Grade 3.

Non-Hematologic Toxicity

CONFIDENTIAL

STUDY DRUG: QUIZARTINIB
PROTOCOL DATE: 10 AUGUST 2020

DEVELOPMENT INNOVATIONS STUDY NUMBER: AML 48
VERSION 4.0

Grade 3 or 4 non-hematologic toxicity that is at least possibly related to quizartinib and persisting >48 hours without improvement to \leq Grade 2 or without waiting 48 hours if in the Investigators judgment the AE poses a serious risk to the patient:

- Dosing will be interrupted for up to 28 days.
 - If toxicity improves to Grade ≤ 1 within 28 days, treatment may be resumed at the previous dose.
 - If toxicity improves to Grade ≤ 2 within 28 days, treatment may be resumed at a reduced dose (1 level) (See Table 2).
 - If toxicity does not improve/resolve within 28 days, then quizartinib will be discontinued.

Hepatic Events and Liver Enzyme Elevation

Elevation of liver enzymes that meet the criteria below should be investigated and the cause identified when possible:

- ALT $>8 \times$ ULN; or
- AST or ALT $>5 \times$ ULN for more than two weeks; or
- ALT or AST $>3 \times$ ULN, but not reaching the limits in the above criteria, in combination with clinical symptoms suggestive of hepatitis; or
- ALT or AST $>3 \times$ ULN with TBL $>2 \times$ ULN*
 - Combined elevations of ALT or AST with TBL as described above will be treated as Adverse Events of Special Interest and reported as per Section 11.2.*

Once the cause of liver enzyme elevation is identified, remove or treat the contributing cause. If the above criteria are met and the elevation is considered to be related or possibly related to quizartinib, then quizartinib dosing should be interrupted.

Liver enzyme level testing will be repeated at least weekly, or more frequently, based on degree of hepatic laboratory abnormality. If the liver enzyme levels return to baseline levels, quizartinib may be resumed at the full dose. If toxicity does not improve/resolve within 28 days, then quizartinib will be discontinued.

Upon resumption of quizartinib, if liver enzyme elevations recur, treatment may be resumed at a reduced dose following return to baseline levels.

Liver Safety Monitoring and Evaluations

Any patient who temporarily interrupts or permanently discontinues quizartinib due to confirmed liver enzyme abnormalities and/or jaundice in the absence of a known cause, must have an evaluation to determine the cause of the event.

Evaluation may include the following depending on the clinical situation:

- Medical history and physical exam, including focus on medications and substances used: alcohol, acetaminophen, azole antifungals, change in medication dosages, new

CONFIDENTIAL

medications added, over the counter medication use and recreational drug use. Check for change in diet or use of dietary supplements

- Abdominal ultrasound
- Hepatitis B, and C screening (hepatitis B surface antigen, and anti-hepatitis C virus plus viral titer), antinuclear antibody and anti-Smith antibody, cytomegalovirus, Epstein Barr virus
- Additional evaluations as deemed appropriate by the Investigator to exclude other causes of liver enzyme and bilirubin elevations
- All laboratory results, including local laboratory reference ranges are to be recorded.

Myelosuppression (Maintenance Phase)

Quizartinib should be reduced or dosing interrupted (See Table 3) at the Investigator's discretion if:

- The patient has been treated for a minimum of 2 cycles;
- Platelet count is $<100,000/\text{mm}^3$ and $\text{ANC} \leq 1000/\text{mm}^3$; and
- There is no evidence of relapse.

The dose of quizartinib may be reduced stepwise from 60 mg/day to 30 mg/day to 20 mg/day. For patients experiencing myelosuppression requiring dose reduction while taking a dose of 30 mg/day (20 mg/day in patients receiving a strong CYP3A4inhibitor), dosing will be interrupted.

CONFIDENTIAL

STUDY DRUG: QUIZARTINIB
PROTOCOL DATE: 10 AUGUST 2020

DEVELOPMENT INNOVATIONS STUDY NUMBER: AML 48
VERSION 4.0

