3.3 Discontinuation from Study Treatment

Patients will be discontinued from study treatment for any of the following reasons:

- Irreversible or intolerable toxicity or abnormal laboratory values thought to be related to drug toxicity
- Conditions requiring therapeutic intervention not permitted by the protocol
- Intercurrent illness (this will be at the Investigator's discretion)
- Inability of the patient to comply with study requirements
- Patient requests to discontinue treatment, but agrees to finish study procedures
- Patient withdraws consent from the study and is discontinued from the study
- Non-compliance/lost to follow-up
- Pregnancy and breastfeeding
- Further participation would be injurious to the patient's health or well-being, in the Investigator's medical judgment

CONFIDENTIAL

STUDY DRUG: QUIZARTINIB
 PROTOCOL DATE: 10 AUGUST 2020

DEVELOPMENT INNOVATIONS STUDY NUMBER: AML 48
 VERSION 4.0

- The study is terminated by the Sponsor, Sarah Cannon Development Innovations (“Development Innovations”) or the Institutional Review Board (IRB)

After discontinuation from protocol treatment, patients must be followed for adverse events (AEs) for 30 days after their last dose of study drug. All new AEs occurring during this period must be reported and followed at the site until resolution for AEs attributed to the study medication(s).

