8. DOSE MODIFICATIONS

If toxicity occurs, the toxicity will be graded using the NCI CTCAE Version 5, and appropriate supportive care treatment will be administered to decrease the signs and symptoms thereof. Dose adjustments will be based on the organ system exhibiting the greatest degree of toxicity.

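### In the text available, Appendix F sets no automatic permanent stop for Torsade or polymorphic VT when QTcF is 500 msec or less and has risen by 60 msec or less

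*Combined protocol and SAP*

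**What the plan says.** Appendix F grades QTcF prolongation and attaches an action to each grade.

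- **Grade 2** (average of triplicate readings above 480 msec): "The dose will be reduced without interruption". Afterwards the "dose may be resumed at the previous level in the next cycle" if QTcF has fallen to within 30 msec of baseline or below 450 msec. A patient already on 20 mg/day is instead interrupted for up to 14 days.
- **Grade 3** (average of triplicate readings above 500 msec): dosing is interrupted for up to 14 days. If QTcF recovers, "treatment may be resumed at a reduced dose (See Table 2").
- **Grade 4**: QTcF above 500 msec or more than a 60 "msec change from baseline, and Torsade de pointes or polymorphic ventricular tachycardia or signs/symptoms of serious arrhythmia". The action is permanent discontinuation.

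A separate Non-Hematologic Toxicity rule in Appendix F covers Grade 3 or 4 events at least possibly related to quizartinib. It applies when the event persists beyond 48 hours without improving to Grade 2 or lower, or "without waiting 48 hours if in the Investigators judgment the AE poses a serious risk to the patient". Dosing is interrupted for up to 28 days. If the event improves to Grade 1 or lower "within 28 days, treatment may be resumed at the previous dose"; if it improves only to Grade 2, restart is one dose level lower.

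Section 8 adds: "Dose adjustments will be based on the organ system exhibiting the greatest degree of toxicity". Section 3.3 opens its general list with "Patients will be discontinued from study treatment for any of the following reasons". The list includes intolerable toxicity and further participation that the investigator considers injurious. It does not name arrhythmia.

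**The concern.** Safety is a primary objective (Section 2.1), and Section 7.5.1 identifies ventricular arrhythmia and Torsade as the feared consequence of quizartinib's effect on QTc. One would expect drug-related Torsade to end quizartinib treatment whatever the ECG interval recorded around it. Grade 4 instead makes the stop depend on a QTcF condition as well. A patient whose Torsade falls below both limits goes to rules that permit restart.

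What is at stake is the safety of an individual patient. Maintenance can run for 24 cycles at up to 60 mg/day (Section 5.2.4), and Section 7.5.1 describes the QTc effect as dose-dependent. The primary response analysis is not affected.

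**Working it through.** The plan gives no figure to reproduce. The check is a reading of the rule, followed by simple arithmetic on the msec limits.

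**1. Logic of Grade 4.** The natural reading is (QTcF >500 or rise >60) and (Torsade, polymorphic VT, or signs or symptoms of serious arrhythmia). QTcF above 500 alone cannot be Grade 4, because Grade 3 allows restart after that same value. Reading it that way would not help an event below both limits in any case.

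**2. Other candidate stop rules in the available text.**

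- Section 8.2.1: electrolytes, concomitant drugs and repeat ECGs; no permanent stop.
- Section 11.4.1.1: names Torsade in its heading but gives only monitoring and reporting duties.
- Appendix G, cardiotoxicity: stops CPX-351, not quizartinib.
- Appendix F, recurrent Grade 3 at 20 mg/day: a stop based on QTcF alone.
- Appendix F, Non-Hematologic Toxicity: stops quizartinib if the event does not improve within 28 days; a resolved arrhythmia would not meet this.
- Section 3.3: mandatory once a listed reason is met, but whether it is met is a judgment.

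**3. Where the gap meets the Grade 2 rung.** Inputs: Grade 2 begins above 480 and Grade 3 above 500; the Grade 4 limits are >500 or a rise >60 (Appendix F); baseline is at most 450 (Section 3.2).

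- Highest QTcF that escapes Grade 4 = min(500, baseline + 60).
- Whole-msec Grade 2 values (481 to 500) that escape = min(500, baseline + 60) − 480, not below 0. This equals min(20, max(0, baseline − 420)).

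| Baseline (msec) | Highest escaping QTcF | Grade 2 values that escape, of 20 |
|---|---|---|
| 420 | 480 | 0 |
| 421 | 481 | 1 |
| 425 | 485 | 5 |
| 430 | 490 | 10 |
| 435 | 495 | 15 |
| 440 | 500 | 20 |
| 450 | 500 | 20 |

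On the Grade 2 rung the gap is confined to baselines 421 to 450. At QTcF 480 or less with a rise of 60 or less, Grade 4 is not met either. The only QTcF rung left there is Grade 1, which continues the same dose. That region is not counted because Appendix F prints no Grade 1 limit.

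**4. Worked case.** Baseline 440, QTcF 495, Torsade. The rise is 495 − 440 = 55, which is not above 60, and 495 is not above 500. Grade 4 is not met. Since 480 < 495 ≤ 500, the QTcF value is Grade 2.

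**5. Which action then governs.**

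- Torsade is an adverse event in its own right. If it is graded 3 or 4 and at least possibly related, and it persists or is judged a serious risk, the non-hematologic rule interrupts dosing. Section 8 favors this stricter action over the Grade 2 reduction. Restart is then permitted, at the previous dose if the event has improved to Grade 1 or lower.
- The Grade 2 action governs only if the event is graded below 3, is called unrelated, or improves within 48 hours and is not judged a serious risk.

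Neither path ends in an automatic permanent stop once the event has resolved.

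**The case against.** The strongest reply is that nothing obliges anyone to re-dose after Torsade. Restart is permissive, and Section 3.3 is mandatory once toxicity is judged intolerable or participation injurious. A life-threatening event is also an SAE, reportable within 24 hours (Sections 11.1.2 and 11.2), and Section 11.4 treats Torsade as an event of special interest, so the sponsor would learn of it quickly. All of this stands and lowers the severity. None of it sets the outcome for the event.

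A reader might infer that the plan normally manages Torsade by lowering the dose without a break. The documents do not support that: the non-hematologic rule and Section 8 make interruption the likely path.

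A reader might also set the gap against Section 3.2, where a history of Torsade or VT bars entry, and call the plan contradictory. That goes too far. Entry limits here are stricter than continuation limits (QTcF of 450 or less to enter, 470 or less to continue in maintenance under Section 6.4.4.1). Section 7.5.1 also advises caution, not prohibition, where there is a history of ventricular arrhythmia or Torsade.

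The QTcF link has a plausible purpose. Section 7.5.1 describes cardiac arrests in the setting of hypokalemia, sepsis or multi-organ failure, and a QTcF condition may help separate drug effect from other causes. That argues for keeping the link for arrhythmia in general. It is weaker for Torsade or polymorphic VT that the investigator already considers possibly drug-related.

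**Conclusion.** The point holds as a low-severity wording gap. Drug-related Torsade or polymorphic VT below both Grade 4 limits has no automatic permanent stop, and after a likely interruption the rules permit restart, possibly at the previous dose.

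The msec counts describe the reach of the rule, not a probability. The documents give no rate for events below the limits. Section 7.5.1 reports no Torsade among 241 quizartinib patients in the Phase 3 study at 30 or 60 mg. It reports one case in the other completed studies, at 90 mg and associated with QT prolongation. About 34 patients are planned here, so the event is expected to be very rare.

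The conclusion rests on these assumptions:

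- The event would be graded 3 or 4 and called at least possibly related. The protocol prints no grade for Torsade.
- The Grade 4 limits use the triplicate average, as Grades 2 and 3 do. The Grade 4 line does not say so; if a single reading counts, the gap is narrower.
- The unavailable text contains no stop rule. Part of Section 7.5.1, next to the QTc discussion, was not available for this review. It would therefore be too strong to say that no such rule exists anywhere in the plan, although Section 7.5.1 itself refers to Section 8 and Appendix F for specific dosing instructions.

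**What to change.** Keep the Grade 4 line and add one line to Appendix F:

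*Torsade de pointes, or polymorphic VT, at least possibly related to quizartinib, at any QTcF: permanently discontinue quizartinib. This overrides the Grade 1 to 3 QTcF rules and the Non-Hematologic Toxicity restart rule.*

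Leave other signs or symptoms of serious arrhythmia under the existing QTcF-linked rule. Section 7.5.2 lists arrhythmia of any kind among CPX-351 reactions with an incidence of at least 25%, so an unconditional stop for all of them would be too broad. The line still leaves relatedness to the investigator and does not extend to ventricular fibrillation.

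The change needs no new procedures or data. Its cost is an occasional earlier permanent stop in a patient who might otherwise have restarted. It is a cheap improvement.

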Appendix G Management of CPX-351-Related Adverse Events

NCI CTCAE Grade	CPX-351 Action
Cardiotoxicity	Discontinue CPX-351 immediately without resumption
Hypersensitivity Grade 1	Once symptoms resolve, reinitiate infusion at half the prior rate of infusion. Consider premedication with antihistamines and/or corticosteroids for subsequent doses.
Hypersensitivity Grade 2	Do not reinitiate infusion. For subsequent doses, pre-medicate with antihistamines and/or corticosteroids prior to initiating infusion at same rate.
Hypersensitivity Grade ¾	Permanently discontinue treatment, treat according to the standard of care to manage symptoms, and monitor patient until symptoms resolve.
Neutropenia lasting ≥56 days	Proceed to maintenance therapy with quizartinib
Thrombocytopenia lasting ≥56 days	Proceed to maintenance therapy with quizartinib

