Study Drug, Dose, and Mode of Administration:	
Induction phase: CPX-351 (daunorubicin 44 mg/m² IV and cytarabine 100 mg/m² IV) will be given on Days 1, 3, and 5 followed by 30 mg quizartinib by mouth (PO) once daily on Days 8-21. Patients with an incomplete response, but a >50% reduction in the blast count/cellularity ratio compared to the most recent bone marrow (BM) biopsy prior to treatment, should receive one additional cycle of induction therapy (re-induction) with CPX-351 (daunorubicin 44 mg/m² IV and cytarabine 100 mg/m² IV) on Days 1 and 3 only. Re-induction will begin after a 72-hour washout period from the last dose of quizartinib. During re-induction, treatment with quizartinib will resume on Day 6 and continue through Day 21. Any patient with neutropenia or thrombocytopenia lasting ≥ 56 days from the initiation of CPX-351 will not receive consolidation and will instead proceed to the maintenance phase.
 
Consolidation phase: At the Investigator's discretion, patients who achieve CR and do not proceed to an alloHCT or other CT intervention will proceed to the consolidation phase beginning 7 days (± 7) after neutrophil recovery (ANC >1000/μL). Administer up to 2 consolidation cycles of CPX-351 (daunorubicin 29 mg/m² IV and cytarabine 65 mg/m² IV) on Days 1 and 3. Begin quizartinib 30 mg PO once daily on Days 6-21.
 
Maintenance phase: Maintenance dosing of quizartinib will begin at 30 mg/day on Days 1-14, and if there are no non-hematologic Grade ≥ 3 toxicities, the quizartinib dose will increase to 60 mg/day on Day 15. The maintenance phase is a 28-day cycle beginning 7 days (± 7) after neutrophil recovery (ANC >1000/μL) from the consolidation phase or induction phase. Patients will receive quizartinib once daily for a total of 24 cycles or until disease relapse

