5.2.2 Induction Phase

Treatment consists of CPX-351 (liposomal daunorubicin $44 \text{ mg}/\text{m}^2$ IV and cytarabine $100 \text{ mg}/\text{m}^2$ IV) on Days 1, 3, and 5 followed by quizartinib (30 mg by mouth [PO] once daily) on Days 8-21. If there is a PR at the recovery BM biopsy, patients may be re-treated with one additional induction therapy (re-induction) with CPX-351 (daunorubicin $44 \text{ mg}/\text{m}^2$ IV and cytarabine 100

CONFIDENTIAL

mg/m² IV) on Days 1 and 3. Quizartinib (30 mg by PO once daily) will resume on Day 6 and continue through Day 21. If re-induction is required, a minimum 72-hour period is necessary between the dose of quizartinib on Day 21 and the administration of CPX-351 with re-induction.

If it is believed by the PI and/or sub-investigator that a patient with prolonged Grade ≥ 3 toxicity after the induction phase would be likely to experience additional toxicities during the consolidation phase, the patient could bypass the consolidation phase and proceed to a cellular intervention or the maintenance phase. Any patient with neutropenia or thrombocytopenia lasting ≥ 56 days from the initiation of CPX-351 will not receive consolidation and will instead proceed to the maintenance phase.

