5.2.4 Maintenance Phase

The maintenance phase consists of 28-day cycles. Patients will receive quizartinib once daily for a total of 24 cycles or until disease relapse. Maintenance dosing of quizartinib will begin at 30 mg PO once daily on Days 1-14, and if there are no non-hematologic Grade ≥ 3 toxicities and QTcF is maintained ≤ 450 msec, the quizartinib dose will increase to 60 mg/day on Day 15. If consolidation therapy is not advised at all or if only 1 cycle of consolidation is advised based on prolonged toxicities, maintenance therapy will begin 7 days (± 7) after neutrophil recovery (ANC $> 1000/\mu\text{L}$) from the consolidation phase or induction phase.

Patients who proceed to alloHCT or other CT intervention after consolidation will resume quizartinib maintenance no earlier than Day 30 from the intervention or transplant. If ≥ 2 CT interventions (e.g., repeat DLI) are planned after maintenance, a 28-day hold is acceptable, with resumption of quizartinib with the next cycle. If the patient is on quizartinib prior to HCT or CT intervention, quizartinib should be discontinued 7 days prior if a conditioning therapy is utilized. If proceeding to a CT intervention without conditioning therapy (e.g., DLI), quizartinib should be discontinued one day prior to CT intervention.

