8.3.1 Criteria and Procedures for Dose Interruptions and Adjustments of CPX-351

If a patient develops non-hematologic Grade ≥ 3 AE(s) without resolution by 28 days from the first administration, or develop prolonged hematologic toxicities Grade ≥ 3 without count recovery 56 days or longer from first administration, the AEs will be considered severe AEs. However, this will not remove the patient from staying on study to receive quizartinib unless the PI believes quizartinib will exacerbate or prolong the toxicity.

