- d **Maintenance:** Maintenance dosing of quizartinib will begin at 30 mg/day on Days 1-14, and if there are no toxicities and QTcF is maintained ≤450 msec, will increase to 60 mg/day on Day 15. The maintenance phase is a 28-day cycle beginning 7 days (± 7 days) after neutrophil recovery from the consolidation phase or induction phase. Patients will receive quizartinib once daily for a total of 24 cycles or until disease relapse. Patients who proceed to alloHCT or other CT intervention **after** consolidation will resume quizartinib maintenance 30-60 days from the intervention for a total of 24 cycles or until disease relapse. If the patient is on quizartinib prior to HCT or CT intervention, quizartinib should be discontinued 7 days prior if a conditioning therapy is utilized. If ≥2 CT interventions (e.g., repeat DLI) are planned after maintenance, a 28-day hold is acceptable, with resumption of quizartinib with the next cycle (see Section 5.2.4).
- e Informed consent must be obtained prior to the initiation of any screening test or procedure.

CONFIDENTIAL

STUDY DRUG: QUIZARTINIB
 PROTOCOL DATE: 10 AUGUST 2020

DEVELOPMENT INNOVATIONS STUDY NUMBER: AML 48
 VERSION 4.0

- f The screening medical history, physical examination, vital signs, ECOG performance status, and triplicate ECGs, TTE/MUGA, baseline signs and symptoms and safety laboratory tests (including pregnancy and virus testing [hepatitis serology (Hepatitis B surface antigen and antibody and Hepatitis C antibody), HIV-1, 2]) should be done following written consent and prior to initiation of therapy.
- g Physical examination will include measurements of height (screening only) and weight.
- h Vital signs will include resting heart rate, blood pressure, respiratory rate, and temperature.
- i Patients will receive a lumbar puncture during pre-transplant workup, per institutional practices and following site-specific standard operating procedures within the first 2 weeks on study treatment. No further intrathecal (IT) chemotherapy is required in this study if there is no evidence of disease. In patients who have CNS disease involvement, IT chemotherapy should continue every 4 days (± 1 day) until disease clearance, followed by every 7 days (± 2 days) for 2 additional administrations. Thereafter, administer IT chemotherapy every 28 days (± 7 days) for at least 12 cycles (see Section 6.3).

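### For patients with prolonged neutropenia, the protocol is inconsistent on whether neutrophil recovery must come before maintenance quizartinib

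*Combined protocol and SAP*

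**What the plan says.** Four places move a patient with prolonged neutropenia towards maintenance, or towards more quizartinib, without asking for recovery:

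- Appendix G, for neutropenia (and in a separate row thrombocytopenia) of 56 days or more: "Proceed to maintenance therapy with quizartinib". There is no ANC condition and no cross-reference to Section 5.2.4.
- Section 5.2.2, for either cytopenia lasting 56 days or more from the start of CPX-351: the patient "will not receive consolidation and will instead proceed to the maintenance phase". The synopsis repeats this.
- Section 8.3.1, for Grade 3 or higher hematologic toxicity with counts not recovered at 56 days or later: "this will not remove the patient from staying on study to receive quizartinib unless the PI believes quizartinib will exacerbate or prolong the toxicity".
- Section 5.2.3, after the first consolidation cycle: a CRi patient with persistent ANC below 1000/µL and/or platelets below 50,000/µL, more than 14 days after the recovery marrow, may go to a cellular intervention or to maintenance.

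Three places tie the start of maintenance to recovery:

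- Section 5.2.4, when prolonged toxicity means no consolidation or only one cycle: "maintenance therapy will begin 7 days (± 7) after neutrophil recovery", with recovery set at ANC above 1000/µL.
- The synopsis, with the same interval and threshold.
- Appendix D footnote d: "The maintenance phase is a 28-day cycle beginning 7 days (± 7 days) after neutrophil recovery from the consolidation phase or induction phase". No ANC threshold is given.

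**The concern.** Section 5.2.4 addresses patients whose consolidation is skipped or shortened for prolonged toxicity. Sections 5.2.2, 5.2.3 and Appendix G address largely the same patients. One site could start quizartinib in a patient who is still neutropenic, and another could hold it in an identical patient. Each could cite the protocol.

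Three things are at stake.

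- **Safety.** Section 1.5 names pancytopenia, with possibly prolonged neutropenia and thrombocytopenia, as the most anticipated side effect of the combination. Section 7.5.1 lists myelosuppression with quizartinib, including infections or hemorrhage with fatal outcomes.
- **Secondary results.** Section 2.2 includes time to ANC and platelet recovery and the number of patients able to receive consolidation and maintenance. The maintenance count depends on which rule a site follows. Recovery time under Section 9.10 runs from Day 1 of each CPX-351 cycle with no cut-off when maintenance begins, so quizartinib given before recovery enters that measure. Section 1.5 plans to compare count recovery with prior CPX-351 studies.
- **Attribution.** If quizartinib is restarted during neutropenia, continued cytopenia can no longer be separated into a CPX-351 effect and a maintenance effect.

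**Working it through.** The plan states no figure on this point, so there is nothing to reproduce. The check is textual, with a short calculation for scale.

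**Step 1: the start window.** Section 5.2.4 gives 7 ± 7 days after recovery. Earliest start: 7 − 7 = 0 days. Latest start: 7 + 7 = 14 days. Even the earliest start falls on the day of recovery, so the window never covers an unrecovered patient.

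**Step 2: one patient under each passage.** Take a patient whose ANC has not passed 1000/µL by Day 56 from the start of CPX-351.

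- 5.2.2 and Appendix G: if the patient counts as neutropenic, the route is maintenance. No start day and no ANC condition are given.
- 8.3.1: non-recovery does not stop the patient staying on study to receive quizartinib, subject to PI judgment.
- 5.2.4 and synopsis: maintenance has no start date until ANC exceeds 1000/µL.
- Appendix D footnote d: no start date until recovery, undefined.

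In the parallel case after one consolidation cycle, the ANC trigger in 5.2.3 is persistent ANC below 1000/µL. It leads to a phase that 5.2.4 opens only when ANC is above 1000/µL.

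**Step 3: thresholds.** The 56-day rule does not define neutropenia. Section 9.10 defines delayed neutrophil recovery as ANC below 500/µL, 8.3.1 uses a toxicity grade, and 5.2.3 and 5.2.4 use 1000/µL. A patient between 500 and 1000/µL at Day 56 is therefore unclear on two counts: whether the 56-day rule applies, and whether maintenance may start.

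**Step 4: platelets.** None of the start rules has a platelet condition. A patient with platelets unrecovered at Day 56 and ANC above 1000/µL satisfies both sets of passages.

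**Step 5: scale, illustrative only.** Inputs are 34 patients (synopsis) and 17% with ANC below 500/µL beyond Day 42 in CPX-351 induction (Section 7.5.2). The documents give no Day-56 rate p, so I assume 2% to 17%. The expected number is 34p, and the chance of at least one case is 1 − (1 − p)^34.

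- p = 2%: 34 × 0.02 = 0.7 patients; chance of at least one 50%
- p = 5%: 1.7 patients; 83%
- p = 10%: 3.4 patients; 97%
- p = 17%: 5.8 patients; 99.8%

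These treat all 34 as able to reach maintenance. Section 5.2 sends CR and CRi patients on to consolidation and maintenance. If half respond (the design target) and response is unrelated to neutropenia, the counts halve: 0.5 × 0.7 = 0.3 to 0.5 × 5.8 = 2.9 patients.

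**The case against.** The strongest reply is that the passages do two jobs. The 56-day rule sets the route (skip consolidation) and Section 5.2.4 sets the timing (wait for ANC above 1000/µL). The synopsis carries both sentences in one item, and the summary of changes lists them as added together there. Appendix G is a table of CPX-351 actions, so its entry may mean only that no more CPX-351 is given. Section 8.3.1 may concern retention on study, not dosing.

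Much of this stands. The reading is plausible for 5.2.2 and Appendix G, and it rules out one inference a reader might draw: that the protocol mandates quizartinib at Day 56 in a neutropenic patient. No passage names that day as a start.

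The reply does not settle the matter. The trigger in 8.3.1 is absence of count recovery, and the patient stays on study specifically to receive quizartinib. The ANC trigger in 5.2.3 is non-recovery itself; waiting for ANC above 1000/µL would remove the condition that opened the route. Section 5.2.3 is permissive, and 5.2.4 does cover the one-cycle case, but neither says which prevails. The route-and-timing reading also leaves no provision for a patient whose ANC never exceeds 1000/µL.

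A reader might also infer that myelosuppression in the first two maintenance cycles has no provision, because Appendix F sets the condition "The patient has been treated for a minimum of 2 cycles". That goes too far: Section 8.1 lists myelosuppression as a reason for reduction or interruption with no such limit. The two provisions should agree, but neither governs entry to maintenance.

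**Conclusion.** The inconsistency is real and confined to neutropenia. It rests on the text and does not depend on any assumed rate. The missing elements are precedence between the passages, a provision for ANC that never passes 1000/µL, and an ANC definition for the 56-day rule.

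A reader might extend it to thrombocytopenia, because Appendix G gives both cytopenias the same action. The documents do not support that: isolated thrombocytopenia with recovered ANC meets every start rule, so the 28% prolonged thrombocytopenia quoted in Section 7.5.2 does not measure this conflict.

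The number affected is likely a few of 34 at most. That rests on three assumptions: the Day-42 figure of 17% serves as an upper end for Day 56, a rate seen with CPX-351 carries over to the combination, and about half of patients respond. If quizartinib slows recovery, 17% need not be a ceiling. The primary test (13 or more responses in 30) uses response at the recovery assessment and is unaffected. The matter should be corrected because it concerns a dosing rule with a safety consequence.

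**What to change.** Reconcile the synopsis, Sections 5.2.2, 5.2.3, 5.2.4 and 8.3.1, Appendix D footnote d and Appendix G so that they give one answer to three questions:

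1. Is neutrophil recovery required before maintenance starts in patients with prolonged neutropenia?
2. If so, to what defined ANC, and what happens to a patient who never reaches it?
3. What ANC defines neutropenia in the 56-day rule, and how does it relate to the Section 9.10 definition?

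Then align the myelosuppression provisions in Section 8.1 and Appendix F with that choice. The clinical team must choose the rule; this review proposes none.

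The cost is protocol wording in an amendment. Sample size, the response test and the visit schedule need not change on this account.
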